**9.2.5 Immunogenicity objectives**

**9.2.5.1 Primary immunogenicity objective**

The primary immunogenicity objective is to evaluate the immunogenicity of Baxter cell-culture, non-adjuvanted, whole virus H1N1 vaccine, and GSK AS03-adjuvanted, split H1N1 vaccine with respect to Committee of Human Medicinal Products (CHMP) and FDA licensing criteria.

These criteria for adults aged between 18 and 60 years are, for sera collected ‘approximately 3 weeks after vaccination’:

- Number of seroconversions or significant increase in antihaemagglutinin antibody titres >40%
- Mean geometric increase >2.5
- The proportion of subjects achieving an HI titre of  $\geq 40$  or SRH titre of  $25 \text{ mm}^2$  should be >70%

For adults aged over 60 years these criteria are:

- Number of seroconversions or significant increase in antihaemagglutinin antibody titres >30%
- Mean geometric increase >2.0
- The proportion of subjects achieving an HI titre of  $\geq 40$  or SRH titre of  $25 \text{ mm}^2$  should be >60%

The measures of immunogenicity will be calculated as:

*Geometric Mean Titre or Geometric Mean Area:* For each vaccine/age group and each vaccine type, least squares GMTs for HI and MN data (GMAs for SRH data), associated 95% confidence interval and median, minimal, and maximal titre value will be determined for each visit, i.e., days 0, 7, 14, 21, 28, 35, 42, and 180.

**Geometric Mean Ratio (increase):** For each vaccine/age group and each vaccine type, the least squares GMRs will be calculated for the HI, MN and SRH results for the following time points of the study: day 7/day 0, day 14/day 0, day 21/day 0, day 28/day 0, day 35/day 0, day 42/day 0, as well as the associated 95% confidence intervals and the median, minimal, and maximal n-fold increase. Statistical methods used to analyze GMRs will be identical to those described above for GMTs (GMAs).

**Seroconversions:** Percentages of subjects with seroconversion (or significant increase in HI titre). The number and proportion of subjects achieving seroconversion or significant increase in HI titres or SRH area from pre-immunization to each visit after first immunization will be tabulated for each vaccine/age group and each age group.

- Seroconversion is defined as negative pre-vaccination serum (<10 for HI, <4 for SRH) / positive post-vaccination titre ( $\geq 40$  for HI, area  $\geq 25 \text{ mm}^2$  for SRH).
- Significant increase in antibody titre/area is defined as at least a fourfold increase in HI or a 50% increase in area from non-negative pre-vaccination serum ( $\geq 10$  for HI,  $\geq 4$  for SRH).

**Seroprotection:** Percentages of subjects achieving each of the following thresholds: inverse HI titre  $\geq 40$ , SRH area  $\geq 25 \text{ mm}^2$ : The number and proportion of subjects achieving each threshold at each visit will be tabulated for each vaccine/age group and each vaccine type.

All statistical analyses for HI and SRH will be performed on the logarithmically (base 10) transformed values. Titres below the limit of detection for assays will be set to 1 in 5 for HI and  $4 \text{ mm}^2$  for SRH for the purposes of analysis. Original values will be presented in all listings

The above immunogenicity criteria will be applied to sera collected 21 days after completion of vaccination, i.e., 21 days after the second vaccine dose. For pandemic vaccines, all three criteria should be met.

Should both GSK and Baxter vaccines satisfy all three CPMP criteria, we will compare the immunogenicity of the two vaccines (for each vaccine/age group and each vaccine type) in terms of:

- a. Geometric mean titres 21 days after each vaccination;
- b. Geometric mean ratio increases 21 days after each vaccination;
- c. Seroprotection rates 21 days after each vaccination;
- d. Seroconversion rates 21 days after each vaccination.

Comparisons will be made using parametric or non-parametric tests as appropriate for continuous outcomes, and Pearson's chi-square test or Fisher's exact test where appropriate for categorical outcomes. Further analyses using (generalised) linear models will explore the effect of baseline covariates on the outcomes. For populations (a) and (b), analyses using multiple imputation to allow for missing data will also be undertaken as a sensitivity analysis. No formal adjustment will be made for multiple testing but associated P-values will be interpreted cautiously.

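### For SRH, the value substituted for an undetectable area (4 mm²) falls in the non-negative baseline class, so read literally a subject with no detectable antibody counts as a responder at 6 mm² instead of 25 mm²

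*Protocol*

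**What the plan says.** Three rules in Protocol section 9.2.5.1 bear on the SRH responder definition.

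- Negative baseline: "Seroconversion is defined as negative pre-vaccination serum (<10 for HI, <4 for SRH) / positive post-vaccination titre", where positive means at least 40 for HI and at least 25 mm² for SRH.
- Non-negative baseline: a significant increase is "at least a fourfold increase in HI or a 50% increase in area from non-negative pre-vaccination serum", where non-negative means at least 10 for HI and at least 4 for SRH.
- Undetectable values: "Titres below the limit of detection for assays will be set to 1 in 5 for HI and" to 4 mm² "for SRH for the purposes of analysis". The next sentence adds: "Original values will be presented in all listings".

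The protocol states no SRH limit of detection. It does not say whether baseline status is assigned before or after the substitution. Section 9.2.4 lists SRH only as a possible assay.

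**The concern.** The number given to an undetectable SRH serum is the lowest value of the non-negative class. If the substituted data are used for classification, a subject with no measurable antibody leaves the demanding branch (reach 25 mm²) for the lenient one (rise by half).

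The rate affected is the first licensing criterion: above 40% for ages 18 to 60 and above 30% for over 60. Section 9.2.5.1 accepts SRH beside HI in the licensing definitions. Section 4.0 shows that the choice of assay can change a verdict: it cites a trial of an earlier whole-virus H5N1 vaccine from one of the two manufacturers, in which the 7.5 µg dose met all three criteria by SRH but only two by HI.

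Two planned uses look at the response rate alone. Section 9.2.5.2b reports whether a vaccine meets any one criterion 7 and 14 days after each dose. Section 9.2.5.1, item d, compares seroconversion rates between vaccines if both satisfy all three criteria. In that comparison the artefact would favour the vaccine with more post-vaccination areas from 6 to just under 25 mm² among subjects undetectable at baseline.

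**Working it through.** **Inputs (all from 9.2.5.1).**

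| | HI | SRH |
|---|---|---|
| Negative baseline | below 10 | below 4 mm² |
| Non-negative baseline | 10 or more | 4 mm² or more |
| Substitute for undetectable | 5 | 4 mm² |
| Response if negative | 40 or more | 25 mm² or more |
| Response if non-negative | fourfold | 1.5-fold |

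**Step 1, HI as a control.** The substitute 5 is below 10, so the serum stays negative and must reach 40. The rules agree.

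**Step 2, SRH with substituted values.** The substitute 4 is not below 4, so the serum is non-negative. The hurdle is 1.5 × 4 = 6 mm². Post-vaccination areas of 6, 10, 20 and 24.9 mm² all count as responses.

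**Step 3, SRH with original values.** An undetectable serum below 4 mm² is negative and must reach 25 mm². None of the four areas in step 2 is a response. Measured from 4 mm², the required rise is 25/4 = 6.25-fold, against 6/4 = 1.5-fold in step 2.

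**Step 4, dependence on the limit of detection.** With a limit of 4 or 5 mm², no subject remains negative after substitution and the seroconversion branch is empty. With a limit of 3 mm², measured areas from 3 to just under 4 mm² stay negative, but undetectable sera are still moved.

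**Step 5, size.** Inflation = u × q, where u is the share undetectable at baseline and q is the share of those who end from 6 to just under 25 mm². The protocol gives neither. Purely as an assumed illustration, u = 0.5 with q = 0.10 gives 5 percentage points, and u = 0.9 with q = 0.20 gives 18.

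**Step 6, can it change the all-three verdict?** SRH seroprotection (25 mm² or more) does not depend on the floor.
- Ages 18 to 60: passing needs more than 70% at 25 mm² or above. At most 1 − u of the group can come from detectable baselines, so more than 0.70 − (1 − u) = u − 0.30 rose from undetectable and are true seroconverters. At u = 0.70 or more this already exceeds 40%.
- Over 60: the corresponding share is 0.60 − (1 − u) = u − 0.40, which exceeds 30% over the same range.
- Below u = 0.70: a false pass needs seroprotection met while the true response rate is at or below its threshold. More than 0.70 − 0.40 = 0.30 of the group (0.60 − 0.30 = 0.30 in over 60s) must then be seroprotected non-responders. All of them need a non-negative baseline above 25/1.5 = 16.7 mm². As a share of those with detectable baselines this exceeds 0.30/(1 − u): 0.30/0.5 = 60% at u = 0.5, and 0.30/0.4 = 75% at u = 0.6.

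**The case against.** The strongest reply is that the substitution sentence follows the one on log transformation, where a log needs a number, while the responder definitions speak of the pre-vaccination serum itself. On that view baseline is classified from the measured area and the floor serves only geometric means and ratios. This keeps the negative SRH branch populated, whereas the literal reading may leave it empty. The reading is plausible, and HI suggests that undetectable was meant to count as negative. But the stated scope is analysis in general, original values are mentioned only for listings, and nothing fixes the order of the two steps. A programmer following the text could reach 6 mm².

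The reply is also right that SRH may never be run, that the interim analyses in 9.2.7 use HI and MN only, and that retained original values allow correction without new data. These points limit the consequence but do not reconcile the rules.

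Two stronger readings are not supported. A reader might infer that every SRH-negative subject is reclassified. That needs a limit of detection of at least 4 mm², which the protocol does not give. A reader might also infer that a vaccine could be declared to meet the licensing criteria on trivial rises. Section 9.2.5.1 requires all three criteria for pandemic vaccines, and seroprotection largely blocks this.

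**Conclusion.** The rules conflict as written. If the substituted value is used for classification, the SRH hurdle for an undetectable baseline falls from 25 to 6 mm². That figure is exact and rests on no outside assumption.

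The consequence is narrower. If SRH is run, three results are exposed: the SRH seroconversion or significant-increase rate, the by-criterion kinetics results, and the between-vaccine comparison of SRH seroconversion rates. HI results and SRH seroprotection are unaffected. The Day 42 all-three verdict cannot be changed by the artefact when 70% or more are undetectable at baseline. Below that, a change needs a large share of detectable-baseline subjects to start above 16.7 mm² and end seroprotected without a 50% rise. The inflation in percentage points cannot be derived from the protocol.

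**What to change.** Add one sentence to 9.2.5.1: the 4 mm² floor applies to geometric mean areas and ratios, and baseline SRH status is classified from the original value, with undetectable sera counted as negative. Defining negative as 4 mm² or less and non-negative as above 4 mm² has the same effect, apart from a measured area of exactly 4 mm². Either restores the 25 mm² hurdle.

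Do not solve this by lowering the substitute, for example to 2 mm². That would double the area ratio of each subject who goes from undetectable to detectable, and so multiply the group geometric mean ratio by up to 2^u: 2^0.5 = 1.41 at u = 0.5 and 2^0.9 = 1.87 at u = 0.9. The criteria of a mean increase above 2.5 and above 2.0 would become easier to meet.

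The cost is a sentence of text, with no new data or samples. It should be settled before any SRH results are seen.

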## **STUDY SYNOPSIS**

### **TITLE OF STUDY:**

A randomised, partially observer-blind, multi-centre, head-to-head comparison of a two dose regimen of Baxter and GSK H1N1 pandemic vaccines, administered 21 days apart.

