## **9.2 Statistical methods, sample size, and analyses**

### **9.2.1 Sample size**

The aim of the trial is to establish whether GSK and Baxter vaccines satisfy all three CPMP criteria, and if so compare them in terms of immunogenicity (for each vaccine/age group and each vaccine type). The sample size is in line with standard practice. The protocols for seasonal EU vaccine clinical trials and the criteria for assessment have been standardised within the EU. They stipulate that trials should be done with groups of at least 50 subjects. We will recruit 60 per group, allowing for up to 17% dropout. This will enable for example the trial to detect a 10% to 20% difference in seroprotection and seroconversion rates at the 5% significance level with 80% power.

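### The formal comparison of the two vaccines runs only if both meet all three CHMP criteria on the Day 42 data, so it can be dropped, or shrunk towards zero, when one vaccine is near or below a threshold

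*Protocol*

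**What the plan says.** The synopsis title describes a "head-to-head comparison of a two dose regimen of Baxter and GSK H1N1 pandemic vaccines". The primary objective (synopsis and section 5.0) is performance of each vaccine against the CHMP and FDA licensing criteria.

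Section 9.2.5.1 lists three criteria. For ages 18 to 60 they include "Number of seroconversions or significant increase in antihaemagglutinin antibody titres >40"% and "Mean geometric increase >2.5", with seroprotection above 70%. For those over 60 the thresholds are 30%, 2.0 and 60%. The criteria are applied to sera taken at Day 42, "i.e., 21 days after the second vaccine dose", and all three should be met.

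The section then sets the condition: "Should both GSK and Baxter vaccines satisfy all three CPMP criteria, we will compare the immunogenicity of the two vaccines". The comparison covers geometric mean titres (GMT), geometric mean ratios (GMR), seroprotection and seroconversion, each 21 days after each vaccination. Section 9.2.1, and the synopsis under Statistical Hypothesis, give the trial's aim in the same conditional form: to "establish whether GSK and Baxter vaccines satisfy all three CPMP criteria, and if so compare them in terms of immunogenicity". Section 9.2.1 also claims 80% power at the 5% level for a 10% to 20% difference in seroprotection and seroconversion rates.

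The document does not say what is done if a vaccine fails, or whether the condition is applied within each age group or to each vaccine overall.

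**The concern.** Whether the comparison takes place depends on the outcome being compared. Two consequences follow.

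First, if either vaccine misses one criterion, the protocol provides no formal comparison of the four measures in 9.2.5.1. Section 4.0 gives the absence of head-to-head data, and uncertainty over whether one preparation has advantages, as part of the rationale. Section 9.2.7 says results are meant to inform the Department of Health's vaccination strategy.

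Second, if both pass, the weaker vaccine's results have been selected for being high, so the observed difference understates the true one.

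A failure is not far-fetched on the protocol's own evidence. Section 4.0 reports that an earlier non-adjuvanted whole-virus H5N1 vaccine from the same manufacturer, at 7.5 µg, met all three criteria by single radial haemolysis (SRH) but only two by haemagglutination inhibition (HI). HI is a planned assay here; SRH is only a possibility.

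**Working it through.** **The protocol's own figure.** Section 9.2.1 recruits 60 per group and allows 17% dropout: 60 × 0.83 = 49.8, about 50 evaluable. It gives no base rates, so the 10% to 20% range cannot be confirmed. With a two-sided 5% test and pooled variance, power = Φ{[d − 1.96√(2p̄(1−p̄)/n)] / √[(p₁(1−p₁)+p₂(1−p₂))/n]}. For 95% v 75% and n = 50: (0.20 − 1.96 × 0.0714) / 0.0686 = 0.876, so power is 0.809. For 90% v 70% it is 0.711. Ten points reaches 80% only when ages are pooled (150 per arm) at high rates: 85% v 95% gives 0.826. The figure is not disputed here. It matters because it shows that a between-vaccine difference was a design target.

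**Effect of the condition.** Inputs from the protocol: 50 evaluable per arm and seroprotection thresholds of 70% and 60%. Assumptions: the seroprotection criterion alone, and a better vaccine truly at 90%. With n = 50, an observed rate above 70% needs at least k = 36 responders; above 60% needs k = 31.

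- P(comparison runs) = P(X_A ≥ k) × P(X_B ≥ k), with X binomial.
- Mean difference when it runs = E[X_A/50 | X_A ≥ k] − E[X_B/50 | X_B ≥ k].

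Example with the 70% threshold and a weaker vaccine truly at 65%: P(X_A ≥ 36) = 0.9999 and P(X_B ≥ 36) = 0.188, so the comparison runs in 19% of trials. The conditional means are 0.900 and 0.746, a difference of 0.154 against a true 0.25.

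| Threshold | Weaker vaccine, true rate | Comparison runs | Mean observed difference | True difference |
|---|---|---|---|---|
| 70% | 65% | 19% | 15 points | 25 |
| 70% | 70% | 45% | 14 | 20 |
| 70% | 75% | 75% | 12 | 15 |
| 70% | 80% | 94% | 9 | 10 |
| 60% (over 60) | 60% | 45% | 24 | 30 |
| 60% (over 60) | 65% | 73% | 22 | 25 |
| 60% (over 60) | 70% | 92% | 19 | 20 |
| 60% (over 60) | 75% | 99% | 15 | 15 |

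**Power.** By exact enumeration with Pearson's chi-square (n = 50, 70% threshold), for 90% v 70% power is 73% without the condition. With it, the chance of both running the comparison and detecting the difference is 23%. For 95% v 75% the figures are 85% and 60%.

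**Applied to all ages pooled (150 per arm, 70% threshold, better vaccine 90%).** A weaker vaccine at 70% is compared in 47% of trials (16.8 points against 20), at 75% in 91% (14.3 against 15), and at 80% in 99.8% (no visible bias).

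**All three criteria.** A simulation of log10 HI titres (assumed SD 0.6, assumed baseline titres, 20,000 trials) gives the same pattern: a true GMT ratio of 5.0 is seen on average as 4.3, with the comparison running in 39% of trials; 3.6 as 3.4 (85%); 2.5 as 2.5 (99%).

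**Type I error.** With equal vaccines at 75% (n = 50, 70% threshold), rejection given that the comparison runs is 1.3%, against 5.1% without the condition.

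**The case against.** The best defence is that the primary objective concerns licensing criteria, not superiority, and that objective is answered even when one vaccine fails. That is so. However, 9.2.5.1 places the comparison under the primary objective, 9.2.1 names it in the aim and gives it power, and the title announces it. Nor does the condition protect an error rate: the protocol makes no multiplicity adjustment.

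A second defence is that much remains. Section 9.2.5.1 gives GMTs and GMRs with 95% confidence intervals, and tabulates seroconversion and seroprotection, per vaccine and without condition. Section 9.2.5.3 explores vaccine type in (generalised) linear models. Section 9.2.5.2 plans comparisons of secondary measures with no both-pass rule, and section 9.2.7 plans unconditional interim analyses. This stands. A reader might infer that the Department of Health would be left without an answer; the documents do not support that.

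A reader might also infer that the comparison is cancelled whenever one vaccine is clearly worse. It is not: the trigger is a missed threshold. A vaccine truly at 80% against 90% is compared in 94% of trials. Conversely, the comparison is also lost if both vaccines fail.

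Nor do the P-values become too liberal; under equality the test is conservative. The unadjusted tests named in the same section ("Comparisons will be made using parametric or non-parametric tests as appropriate for continuous outcomes, and Pearson's chi-square test or Fisher's exact test") are a separate matter: models with baseline covariates are planned as well, and which analysis leads is commonly settled in the SAP.

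**Conclusion.** The concern holds in this limited form. The condition is stated three times, uses the Day 42 data that are then compared, and conflicts with the title, the rationale and the stated power. Following it as written removes the pre-specified formal comparison whenever either vaccine misses any criterion.

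The size depends on where the weaker vaccine lies. Exactly at a threshold, the comparison runs in about 45% of trials and the difference shrinks by about 6 points (14 against 20 at the 70% threshold, 24 against 30 at the 60% threshold). Ten points above the threshold, it runs in 92% to 94% of trials and the loss is about 1 point; further above, it is negligible. These figures rest on 50 evaluable per arm, a better vaccine at 90% and the seroprotection criterion alone. The true rates are assumptions, because the protocol gives none. Requiring all three criteria cannot make the condition easier to meet.

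**What to change.** Delete the both-pass condition in section 9.2.5.1, in section 9.2.1 and in the synopsis under Statistical Hypothesis. State instead that the two vaccines will be compared within each age group and overall, whether or not either meets the criteria. Report GMT ratios, ratios of GMRs, and risk differences for seroprotection and seroconversion, each with a 95% confidence interval, 21 days after each dose. Report performance against the CHMP and FDA criteria separately.

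This also settles the open questions of what happens after a failure and at which level the condition applies. The cost is protocol wording; no extra subjects, visits or samples are needed.

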### **A. BOTH VACCINES ARRIVE AT EACH CENTRE PRIOR TO REGULATORY APPROVAL**

We will use a block randomisation scheme to ensure that balance between vaccines is maintained and all volunteers are randomly allocated to groups. Subjects who meet the study admission criteria will be enrolled into the study and will be assigned a **5 digit subject number**:

The first digit identifies the study site (1 for Leicester; 2 for Nottingham; 3 for Sheffield).

The second digit reflects the age of the subjects on Day 0 (1 for 18-44; 5 for 45-64; and 9 for 65 years and older).

The following three digits identify the subject within the site and will be assigned sequentially, starting with 001 corresponding to the first subject enrolled within each age band.

Thus each centre will have three randomisation lists, each list corresponding to each age band.

Each centre will continue recruiting volunteers within an age band until the tally for the centres reaches a total of 120 subjects for that age band.

Volunteers in each age band will be randomised by a computer generated randomization code (1:1 proportions in block size(s) that will be determined by the statistician to ensure balance across groups). The randomisation code for each age band will be stored in individual, sequentially-numbered envelopes, specific for each centre, and will be opened by the nurse with responsibility for vaccine administration. The type of vaccine for administration will be printed on an adhesive label. The label will be peeled from its backing and entered into an appropriate space in the 'Vaccine Log', ensuring that the instruction and vaccine that is administered actually agree (See below).

Only one study nurse/doctor will be responsible for vaccine administration in each centre. This study nurse/doctor will be un-blinded with respect to the type of vaccine administered; he/she will play no

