#### B. ONLY ONE VACCINE ARRIVES AT EACH CENTRE PRIOR TO REGULATORY APPROVAL:

This scenario is the one most likely to occur. It will be implemented if all regulatory approval is in place, AND only one of the two trial vaccines is available in each centre, AND the second vaccine will not arrive within five days of arrival of the first vaccine. Subjects who meet the study admission criteria will be enrolled into the study and will be assigned a **5 digit subject number**:

As before the statistician would generate three 'randomisation' lists for each centre, with a list for each age band.

As before, the first digit identifies the study site (1 for Leicester; 2 for Nottingham; 3 for Sheffield);  
As before, the second digit reflects the age of the subjects on Day 0 (1 for 18-44; 5 for 45-64; and 9 for 65 years and older);

As before the next three digits identify the subject within the site.

HOWEVER, the distribution of the numbers will be randomised, with the first 60 numbers corresponding to the first vaccine to arrive (Vaccine 1), and the second 60 numbers corresponding to the second vaccine (Vaccine 2).

As an example, the first person to be vaccinated in Leicester could have the number 10054, i.e., with '1' corresponding to Leicester, '0' reflecting that he/she is aged 18-44 years, and '054' being the volunteer's unique trial number.

Each centre will continue recruiting volunteers within an age band until the tally for the centres reaches a total of 60 subjects for that age band for Vaccine 1. The same process will then be carried out with Vaccine 2, when it arrives.

Depending on the interval between arrival of GSK and Baxter vaccines, we will endeavour to ship sera from some volunteers who received Vaccine 2 in the first tranche of sera that was sent for analysis. The laboratory staff will not know when Vaccine 2 arrived and was first given, so will not know whether sera were collected from recipients of GSK or Baxter vaccine.

Vaccinees will not be told which vaccine they receive. They will be instructed to look away, both during preparation and administration of the vaccine. It is essential that volunteers do not see the syringe that is used or whether the vaccine is translucent or cloudy.

As before, only one study nurse/doctor will be responsible for vaccine administration in each centre. This study nurse/doctor will be un-blinded with respect to the type of vaccine administered; he/she will play no other role in the study.

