#### **9.2.5.2 Secondary immunogenicity measures**

The secondary immunogenicity measures are:

- a. To identify whether one or two doses of vaccine are required to satisfy the licensing criteria. We will assess whether either GSK or Baxter vaccine is able to meet all three CPMP criteria 21 days after the first vaccine dose. This will be assessed for each vaccine/age group, and each vaccine type;
- b. To examine the kinetics of the antibody responses to vaccination. This will be measured in terms of the ability of GSK or Baxter vaccine to meet any one, or all three, of the CPMP criteria 7 and 14 days after the first and second doses – for each vaccine/age group, and each vaccine type;
- c. To examine persistence of antibody at 6 months. This will be assessed in terms of the proportion of vaccinees who have inverse HI antibody titres of  $\geq 40$ , SRH areas of  $\geq 25\text{mm}^2$ , and inverse MN antibody titres of  $\geq 40$  and  $\geq 80$ . Antibody persistence will be assessed for each vaccine/age group, and each vaccine type;
- d. To evaluate the breadth of the antibody response to the antigenic variant (if appropriate, i.e., an antigenic drift variant emerges prior to the 2010-2011 influenza season). This will be done using the new antigenic variant as test antigen in HI, MN, and possibly by SRH tests by comparing the above primary immunogenicity measures on days 21 and 42 for each vaccine, by age group, and all age groups combined.

As with the primary immunogenicity outcomes comparisons will be made using parametric or non-parametric tests as appropriate for continuous outcomes, and Pearson's chi-square test or Fisher's exact test where appropriate for categorical outcomes. Further analyses using (generalised) linear models will explore the effect of baseline covariates on the outcomes. For populations (a) and (b), analyses using multiple imputation to allow for missing data will also be undertaken as a sensitivity analysis. No formal adjustment will be made for multiple testing but associated P-values will be interpreted cautiously.

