### 9.2.5.3 Exploratory analyses

The possible effect of previous seasonal influenza vaccination, age, presence of detectable levels of antibody before vaccination, as well as vaccine type – and any interactions will be explored using (generalised) linear models.

If one vaccine is available significantly before the other, then the trial will adopt a sequential allocation procedure switching to randomisation when the second one becomes available. If such a situation arises then the comparisons outlined in 9.2.5.1 will be non-randomised ones and potentially subject to bias (for example due to temporal effects). In this situation the use of date (time) of vaccination will also be used as an explanatory covariate in (generalised) linear models in order to explore the potential impact of this on the trial outcomes.

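### The main between-vaccine comparison is unadjusted: Day 0 titre is left to exploratory models, age band is ignored when ages are pooled, and centre enters no analysis

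*Protocol*

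**What the plan says.** Section 9.2.5.1 provides that, if both vaccines meet all three criteria, "we will compare the immunogenicity of the two vaccines (for each vaccine/age group and each vaccine type) in terms of" geometric mean titres (GMTs), geometric mean ratios (GMRs), seroprotection rates and seroconversion rates, each 21 days after each dose. The method is: "Comparisons will be made using parametric or non-parametric tests as appropriate for continuous outcomes, and Pearson's chi-square test or Fisher's exact test". It continues: "Further analyses using (generalised) linear models will explore the effect of baseline covariates on the outcomes". Section 9.2.5.2 applies the same approach to the secondary measures: "As with the primary immunogenicity outcomes comparisons will be made using parametric or non-parametric tests as appropriate for continuous outcomes".

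Section 9.2.5.3, headed as exploratory, lists the covariates: "The possible effect of previous seasonal influenza vaccination, age, presence of detectable levels of antibody before vaccination, as well as vaccine type", with interactions. Pre-vaccination antibody appears there as detectable or not, rather than as a titre. Centre is not listed there or anywhere else in section 9.

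On allocation, section 7.4 has two scenarios. In A, allocation is blocked: "1:1 proportions in block size(s) that will be determined by the statistician to ensure balance across groups". "Thus each centre will have three randomisation lists, each list corresponding to each age band". In B, all subjects for the vaccine that arrives first are enrolled before those for the other, and the protocol says: "This scenario is the one most likely to occur". Section 9.2.5.3 accepts that the comparisons in 9.2.5.1 would then not be randomised and could be biased by time, and adds vaccination date as a covariate in the exploratory models.

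**The concern.** The protocol goes beyond leaving the method open. It names two-group tests for the comparison and gives covariate adjustment a secondary role. Three things follow.

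- **Precision.** Day 0 titre is measured on everyone, and post-dose titre probably depends on it. Section 4.0 cites cross-reactive neutralising titres of 160 or more in 6% of adults aged 18 to 40 and 33% of those aged 60 and over, so baseline antibody differs between people and rises with age. With about 50 evaluable subjects per group there is little precision to spare.
- **Strata.** Under scenario A the lists are by centre and age band: 3 × 3 = 9 lists. The comparisons within each age group respect age band. The pooled-age comparison does not, and no comparison respects centre.
- **Bias.** Under scenario B the two vaccine groups are recruited in different periods. Section 6.7.1 has frontline staff approached before people outside health care, section 7.4 B fills each age band by a tally across centres, and section 4.0 expects infections to increase from September. Each could make the groups differ in type of subject, centre mix or Day 0 titre. Unadjusted tests would still lead.

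**Working it through.** **Inputs from the protocol.** 60 per vaccine and age group with up to 17% dropout (9.2.1); log10 transformation for HI and SRH, with undetectable HI titres set to 5 (9.2.5.1); 9 lists under scenario A (7.4).

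**Assumptions, none in the protocol.** Correlation r between log Day 0 and log post-dose titre, 0.3 to 0.6. For the pooled-age check, SD of log10 titre 0.6 within strata, centre means of −0.1, 0 and +0.1, and three equally spaced age-band means spanning 0.3, 0.6 or 0.9 log10.

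**The plan's own figures.** 60 × 0.83 = 49.8, so about 50 evaluable per group. The claim of 80% power for a difference of 10 to 20 points cannot be reproduced uniquely, because no base rate is given. With 50 per arm and a two-sided 5% test, 75% versus 95% has 81% power, 70% versus 90% has 71%, and 50% versus 70% has 53%. A 10-point difference reaches 80% only near the ceiling and with ages pooled: 85% versus 95% with 150 per arm has 83%.

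**Gain from baseline adjustment, log titres.** With the unadjusted post-dose comparison set to variance 1, the adjusted comparison has variance 1 − r².

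| r | 1 − r² | 50 per arm is worth | CI narrower by | 80% power becomes |
|---|---|---|---|---|
| 0.1 | 0.99 | 50.5 | 0.5% | 80% |
| 0.3 | 0.91 | 50/0.91 = 55 | 1 − √0.91 = 4.6% | 84% |
| 0.5 | 0.75 | 50/0.75 = 67 | 13.4% | 90% |
| 0.6 | 0.64 | 50/0.64 = 78 | 20% | 94% |

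The last column is Φ[(1.960 + 0.842)/√(1 − r²) − 1.960]. The row for r = 0.1 stands for groups in which most Day 0 titres are undetectable, so that baseline is nearly constant.

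**The GMR comparison.** The fold-rise already uses each subject's baseline. With k = baseline SD divided by post-dose SD, its relative variance is 1 + k² − 2kr.

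- k = 1: 2(1 − r) = 1.40 at r = 0.3 and 0.80 at r = 0.6.
- k = 0.5: 1.25 − r = 0.95 and 0.65.

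The adjusted model has 0.91 and 0.64. It is never worse, but the loss from using the fold-rise ranges from large to negligible depending on k.

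**Pooled-age test under scenario A.** Balanced allocation removes stratum differences from the estimate, but the unadjusted test leaves them in its standard error. The standard error is inflated by √[(σ² + between-stratum variance)/σ²], with σ² = 0.36. The between-stratum variance is 2(spread/2)²/3 for age plus 2(0.1)²/3 = 0.0067 for centre.

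- Spread 0.3: √(0.3817/0.36) = 1.03; true type I error 2Φ(−1.960 × 1.03) = 4.4%.
- Spread 0.6: √(0.4267/0.36) = 1.09; 3.3%.
- Spread 0.9: √(0.5017/0.36) = 1.18; 2.1%.

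A simulation (6,000 runs, 50 per cell, true difference 0.2 log10) agrees: type I error about 4.6%, 3.5% and 2.0%, with power about 81%, 77% and 71%. Adding the strata brings type I error to about 5% and power to about 82%. Adding baseline as well brings power to about 85% (r = 0.3) or 91% (r = 0.5).

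**Rates.** 1 − r² does not apply to seroprotection or seroconversion, and no gain is claimed for them. There the argument is only that the analysis should follow the strata.

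**The case against.** The strongest reply is that the unadjusted tests are valid under randomisation and err on the safe side when ages are pooled. The primary objective sets each vaccine against fixed licensing criteria, which this change does not touch, and the head-to-head comparison takes place only if both vaccines meet all three. All of that stands, and it limits the importance of the point.

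The size of the gain can also be challenged. The protocol gives no correlation or variance. The cited prevalences concern neutralising titres above a cut-off in US adults and do not establish how much of the variance baseline explains. With undetectable HI titres set to 5 and known infections excluded, baseline may hardly vary in younger adults. That stands too, which is why the gain is given as a range that can fall almost to zero.

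The least squares GMTs in 9.2.5.1 suggest a linear model, and its terms could be set in an analysis plan. But the tests named for the comparison carry no covariates, and the protocol calls the models that do further and exploratory. This is a stated choice and not simply an omitted detail.

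A reader might infer that randomisation is ignored throughout, that the test will be picked after the data are seen, or that testing GMT and GMR side by side is an error. The text does not support these readings. Age band is respected in the per-age comparisons, and stratified randomisation applies to scenario A only. The protocol says tests will be used as appropriate, which leaves the choice open without saying when it is made. The GMR is itself a licensing measure and belongs in the report.

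**Conclusion.** The point holds as a recommended improvement. It does not make the planned tests invalid. Sections 9.2.5.1 and 9.2.5.2 lead with unadjusted tests, leave baseline to exploratory models, omit centre altogether and ignore age band in the pooled comparison.

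Under scenario A the cost is precision for log titres: 9% to 36% of the variance for an assumed r of 0.3 to 0.6, less where Day 0 titres are mostly undetectable, plus a conservative pooled-age test whose degree depends on the assumed differences between age bands. Under scenario B, which the protocol expects, the main problem is that a comparison it concedes to be non-randomised has no adjustment in its lead analysis.

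A reader might infer that adjustment would put scenario B right. It would not. If one vaccine's enrolment is finished before the other's begins, vaccine and date are almost completely confounded, and a date term separates them only by assuming the form of the time trend.

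**What to change.** In 9.2.5.1, and by reference in 9.2.5.2:

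- Make the main between-vaccine comparison of titres 21 days after each dose a linear model on log10 titre with vaccine, log10 Day 0 titre, centre and, for pooled ages, age band. Report an adjusted GMT ratio with 95% CI.
- Compare seroprotection and seroconversion by risk differences (for example Mantel-Haenszel) stratified by centre and, for pooled ages, by age band.
- Keep the GMRs for the licensing criteria, and the unadjusted tests as supportive analyses.
- If allocation is sequential, also report the model with vaccination date, label the comparison non-randomised, and state that temporal bias may remain.

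The cost is analysis wording only. Day 0 titre, age, centre and vaccination date are already collected, and sample size, visits and assays are unchanged.
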